## **4. REGISTRATION PROCEDURES**

Patients who are identified as potential candidates for the study will be identified in the Kirklin Clinic or at the Hepatobiliary Tumor Conference. They will be contacted to explain the nature of the study, to obtain written informed consent and to be enrolled in the study. The study coordinator will then schedule the imaging, and complete any subsequent forms.

## **5. STUDY PLAN**

### **5.1 FMISO Administration**

Fluorine-18 labeled misonidazole (FMISO) will be administered as an intravenous injection of less than or equal to: 15 µg of FMISO; 10 mCi of radioactivity; and 10 mL in volume. FMISO will be prepared in UAB Cyclotron PET Production Facility and dispensed from UAB Nuclear Pharmacy. It will be administered to the patient in the PET imaging suite at the UAB Advanced Imaging Facility, in the basement of WTL. The injection will be infused nominally over one minute and followed by a saline flush.

### **Study Procedures and Schedule of Events**

Patients who are identified as potential candidates for the FMISO PET study will be approached to explain the nature of the study and to get their informed consent to be enrolled in the protocol. Imaging will be performed on inpatient or outpatient basis.

All patients entering the study will have had diagnostic CT or MRI scans of the abdomen as part of their cancer staging evaluation.

Imaging Acquisition Procedure for FMISO PET involves the following steps:

1. Baseline vital signs including resting blood pressure, pulse rate, and breathing rate will be measured and recorded within 60 minutes prior to the start of imaging.
2. Women of childbearing potential will receive a urine test prior to the procedure to rule out pregnancy
3. Placement of 1 intravenous catheter for injection of the radiopharmaceutical.

4. Careful patient positioning with the liver centered within the PET/CT scanner field-of-view. The patient will be made as comfortable as possible on the imaging table.
5. Attenuation correction will be obtained using the low dose CT scan on the PET/CT scanner.
6. Intravenous injection of FMISO ( $\leq 15 \mu\text{g}$  (range 7 mCi-10 mCi) not to exceed 10 mCi, followed by saline flush.
7. The patient will be imaged in a dynamic fashion for 30 minutes and then again for a 30-minute static scan after a 60-minute wait period
8. Data analysis: The regional tissue:blood ratio values will be determined and hypoxic volume of the primary tumor and metastases will be calculated.
9. The study team will conduct a 24hr follow up call after FMISO administration to elicit and record any adverse event.

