## 1. OBJECTIVES

This Phase II study will investigate the ability of [F] FMISO (FMISO) to identify hypoxia in HCC and development of increased tumor hypoxia in tumors treated with TACE.

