## **7. STATISTICAL CONSIDERATIONS**

### **7.1 Study Design/Endpoints**

This is a Phase II study of a PET imaging agent, [F]FMISO, in patients with HCC who will be receiving standard care with TACE, and with radiation. The imaging study will not impact the patient's treatment. The objective of this study is to evaluate the potential of [F]FMISO as a non-invasive indicator of tissue hypoxia in HCC patients to provide tumor imaging data.

The primary endpoint is changes in [F]FMISO parameters (HV and T:Bmax) between baseline and follow-up scans. The regional tissue: blood values will be determined and hypoxic volume of the primary tumor and metastases will be calculated. The number of pixels in the tumor volume with a T/B ratio  $\geq 1.2$ , indicating significant hypoxia, will be determined and converted to milliliter units to measure the HV. In each tumor region, we will also locate the pixel with the maximum T/B ratio and include this variable, T/Bmax, in our analysis. HV evaluates the volume of tumor that has crossed the threshold for hypoxia and T/Bmax depicts the magnitude of hypoxia.

The exploratory endpoints include overall survival (OS), disease free survival (DFS) and response to XRT by RECIST, mRECIST or EASL (because enhancement changes are known to better reflect treatment response than size changes) criteria.

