### **7.2 Sample Size/Accrual Rate**

This is a Phase II study in patients with Hepatocellular Carcinoma (HCC). We propose a sample size of 20 patients for this initial clinical trial because of patient recruitment based on low HCC incident from UAB tumor register data. If the results are promising but inconclusive, they will be used to define a larger multi-center trial. We expect to have a full enrollment in 2 years. From the previous study (Rajendran 2006), a significant hypoxia was identified in 58 patients (79%) in head and neck cancer. The mean

FMISO T/Bmax was 1.6 (range 1.0–3.5) and the mean HV was 40.2 mL (range 0–1092). We expect at least 60% hypoxia/uptake (e.g. TB ratio changes from baseline >1.2) will be identified in HCC patients in this study, thus with a size of 20 patients we will be able to have an accurate estimation of patients who will have undertaken of [F] FMISO with ~ 10% error, and produces a two-sided 95% confidence interval with a width equal to 0.448 for each FMISO PET scan. The size will be also able to evaluate pre-post changes of 1.5 effect size for T/Bmax based on the above published data using one group paired t-test with >80% power at 5% alpha level. Due to the nature of exploratory to generate hypothesis data for future study, the intra correlation between FMISO PET scans within the same subject will not considerate in the sample size consideration this time.

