### 7.3 Statistical analysis plan

The primary endpoint analysis of changes in [F]FMISO parameters (HV and T:Bmax) between baseline and 2 follow-up scans will be using paired t-test. Proportion of patients with uptake of [F] FMISO will be reported as N and % and exact 95% confidence interval using the method of Clopper-Pearson. Descriptive analysis such as mean, standard deviation at baseline and follow-up will be estimated with two-sided 95% confidence intervals for all [F]FMISO parameters from PET scans. Longitudinal analysis will be also applied to estimate the changes (slope) between baseline to the first treatment of TACE and sequential treatment of Stereotactic Radiotherapy (SBRT) with auto correlation covariance structure to control patients' intra-correlation. When repeat studies are done sequentially over the course of treatment, changes are expected to be substantial.

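### The plan lists HV and T/Bmax measurement among each scan's own steps, with no masking to time point and no contouring rule, so a reading difference could enter the uncontrolled pre-post change

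*Combined protocol and SAP*

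**What the plan says.** The imaging steps under Study Procedures and Schedule of Events run from baseline vital signs to a 24-hour follow-up call. Step 7 is the dynamic and static acquisition and step 9 is the call. Between them, step 8 reads: "Data analysis: The regional tissue:blood ratio values will be determined and hypoxic volume of the primary tumor and metastases will be calculated".

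Section 7.1 makes the change in HV and T/Bmax between baseline and follow-up the primary endpoint. HV starts from "The number of pixels in the tumor volume with a T/B ratio" at or above 1.2, converted to millilitres. T/Bmax is the highest T/B pixel in each tumour region. Section 7.3 tests the changes from baseline to the two follow-up scans by paired t-test. All patients are in one group.

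On what the team expects, section 7.3 says "When repeat studies are done sequentially over the course of treatment, changes are expected to be substantial", and section 1 lists "development of increased tumor hypoxia in tumors treated with TACE" among the things to be investigated.

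The document does not say who measures the scans, when, in what order, or whether the reader knows the time point. It gives no rule for drawing the tumour volume, for choosing which metastases to include, or for obtaining the blood value.

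**The concern.** With no control group, the whole result rests on follow-up scans being measured in the same way as baseline scans. The threshold and the maximum are fixed, but both operate inside a region that somebody has to draw. If scans are measured one by one as they are acquired, the reader knows whether each one precedes TACE, follows TACE or follows SBRT, and works in a team that expects change.

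A consistent tendency to draw follow-up regions wider or tighter would appear in the results as a change in hypoxia. No later analysis of the recorded values could recover the difference. Section 1 says the findings will be used to evaluate FMISO imaging for guiding therapy and assessing response in a large-scale trial, so a reading artefact could be carried forward.

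**Working it through.** **1. The plan's own power figure.** Section 7.2 states "We propose a sample size of 20 patients for this initial clinical trial" and claims it can evaluate "pre-post changes of 1.5 effect size for T/Bmax" "using one group paired t-test with >80% power at 5% alpha level". Take n = 20, standardised paired effect d = 1.5 and two-sided alpha 0.05 (sidedness is not stated and is assumed here). The noncentrality is 1.5 × √20 = 6.71 on 19 degrees of freedom, which gives power 0.99999. The claim of more than 80% holds, and this point does not alter it.

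**2. How small a shift the test reacts to.** The critical value is t(0.975, 19) = 2.093. An observed mean change of 2.093/√20 = 0.47 SD of the paired difference is therefore significant, whatever its source.

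**3. A pure reading shift with no true change.** Let reading add a constant b, in SDs of the paired difference. The rejection probability is the noncentral-t power at d = b, n = 20:

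| b (SD) | P(p < 0.05) |
|---|---|
| 0 | 0.05 |
| 0.1 | 0.07 |
| 0.2 | 0.14 |
| 0.3 | 0.25 |
| 0.5 | 0.56 |

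For T/Bmax the document gives no SD of the difference. As a stand-in, divide the head and neck range quoted in section 7.2 (1.0 to 3.5, width 2.5) by 6 or by 4, giving 0.42 to 0.63. A shift of 0.3 SD is then about 0.13 to 0.19 T/B units.

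**4. Direction.** With image and blood value held fixed, enlarging a contour can raise HV and T/Bmax or leave them unchanged. It cannot lower either, because no pixel is removed. HV rises only if some of the added rim is at or above 1.2, and T/Bmax rises only if the hottest pixel lies in the rim.

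**5. Contour width and tumour volume.** For a sphere of diameter D whose contour is m wider in radius, the volume ratio is ((D + 2m)/D)³.
- D = 30 mm (the entry minimum): (32/30)³ = 1.21 for 1 mm and (34/30)³ = 1.46 for 2 mm.
- D = 50 mm: (52/50)³ = 1.12 and (54/50)³ = 1.26.

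These are changes in contoured volume. They carry over to HV only if HV scales with that volume, which step 4 shows need not be so.

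**6. Sensitivity of an HV illustration.** Simulation: 20,000 trials, n = 20, paired t-test on raw millilitres, no true change, follow-up HV multiplied by 1.20. Baseline HV is log-normal with log SD 1.0 unless stated. Each row gives the rejection rate for a log-change SD of 0.3 and of 0.5.

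| Assumption | SD 0.3 | SD 0.5 |
|---|---|---|
| Change factor has mean one | 0.34 | 0.09 |
| Change factor has median one | 0.51 | 0.28 |
| Mean one, 40% of patients with zero HV | 0.17 | 0.04 |
| Mean one, baseline log SD 1.5 | 0.18 | 0.05 |

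With no bias, the first row gives 0.04 and 0.05. The 40% figure is the complement of the plan's "We expect at least 60% hypoxia/uptake", used loosely as a share of patients with no measurable HV. The same 20% bias thus yields anything from 0.04 to 0.51, depending on inputs that the document does not supply.

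**The case against.** A reader might infer that the plan prescribes unmasked reading in calendar order. It does not. Step 8 names no reader, time or order; its place in a workflow list is suggestive and no more. Section 5.4 puts the final analysis after accrual, which leaves later batch reading possible. That part of the objection stands: the gap is silence about reading conditions. But batch reading without masking would not protect the endpoint either, and the plan requires neither.

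A reader might also infer that the team expects change in one direction at both follow-up scans. The text does not support that. The statement in section 7.3 has no direction, section 1 presents increased hypoxia after TACE as a matter to investigate, section 2.1.b says TACE's effect on hypoxia is not clearly known, and no direction is given for the scan after SBRT. A one-directional bias on both comparisons is therefore an assumption.

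The fixed threshold and maximum-pixel rule do limit discretion, and no T/B value for surrounding liver is given from which to judge how much of an added rim would count. They leave open the contour, the lesions included and the blood denominator.

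Finally, sections 7.2 and 7.3 describe a small, hypothesis-generating study. That lowers the stakes, but the change in HV and T/Bmax is still its primary endpoint.

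**Conclusion.** The point holds as a gap in measurement procedure. The primary result is an uncontrolled change in two measures taken inside a region with no drawing rule, by a reader whom nothing masks to time point, in a study that anticipates substantial change. Any systematic reading difference between baseline and follow-up would enter the estimate, and the paired test could not tell it from a treatment effect.

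The size is unknown. The 25% false-positive rate for a 0.3 SD shift is exact only under an assumed constant shift and normal differences. The HV simulation ranges too widely to support a claim about magnitude. The document does not support the conclusion that the results will be biased, or that they will be biased upward. No sample-size or power figure changes. The case for acting rests on a cheap safeguard for the primary endpoint.

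**What to change.** Take HV and T/Bmax measurement out of the scan-day steps and describe it in section 7.1 or a short reading procedure:

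- After a patient's last scan (the third, or the last one before withdrawal), give the existing reader that patient's scans together, with dates and scan numbers removed and in random order.
- Apply one pre-specified rule to every scan for drawing the tumour volume, for which lesions are included, and for the blood reference value.
- Lock HV and T/Bmax before the order is revealed.

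The cost is de-identifying and shuffling at most three image sets per patient, plus writing the rule. It needs no extra reader, scan or patient. Values become available later, which does no harm because section 7.1 says the imaging does not influence treatment. Visible post-TACE change may partly reveal the order, so masking will be imperfect and the common contouring rule carries part of the protection. Re-reading a few scans would show how repeatable the measurements are, but is optional.

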#### **5.4 Duration of Follow Up.**

Being an imaging only trial, we will not be seeing the patients in nuclear medicine after the last imaging is completed. We will be able to obtain clinical follow-up information from medical records generated at clinic visits and update our data base at 6 month intervals, for two years. Final analysis will take place at the completion of patient accrual.

**5.5. Data Collection.** Treatment selection is based on current clinical practices.

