## SCHEMA

This Phase II study will investigate the utility of [ $^{18}\text{F}$ ] FMISO in patients with hepatocellular carcinoma (HCC). This trial is designed to test the hypothesis that PET determined [ $^{18}\text{F}$ ]FMISO uptake will indicate tumor hypoxia in patients with HCC treated with trans-arterial chemo-embolization (TACE). We anticipate that [ $^{18}\text{F}$ ] FMISO PET/CT will advance our understanding of the role of hypoxia in HCC prior to treatment and that this knowledge will help design newer combination therapeutic trials for better treatment outcomes.

Adults with HCC and limited hepatic disease eligible for TACE will be enrolled in the study and imaged according to the following schema: After imaging (FMISO 1 and FMISO 2 in the diagram below), patients will be followed for two years or until disease progression. [ $^{18}\text{F}$ ] FMISO PET/CT provides three parameters, tissue hypoxic volume (HV), maximum tissue to blood uptake ratio ( $T:B_{\text{max}}$ ) and tumor blood flow. Both pre-and post-therapy images will be examined to investigate changes in these parameters during the course of TACE treatment.

The study schema is shown below.

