The exploratory endpoints analysis include using cox regression analysis to correlate [F]FMISO parameters with overall survival and progression free survival; and using logistics regression analysis to associate [F]FMISO parameters with clinical response (yes, no). Baseline [F]FMISO, FU [F]FMISO, and changes of [F]FMISO between baseline and FU will be used individually in order to identify if early image of [F]FMISO at baseline, and treatment with TACE alone (FU1) and with radiation (FU2) can predict survival or response. Survival is defined from the time of initial PET scan to the last follow up. Patient's demographics and other prognosis factors will be adjusted in the model. The set of prognostic variables considered in the analysis include standard clinical measures (age, tumor-node-metastasis status), as well as the PET measurements [HV, and FMISO tissue to blood ratio (T/Bmax)]. Due to the high correlation between HV and T/Bmax, and the resulting issue of multicollinearity, these variables will each considered separately with the other prognostic variables. Hazard ratio and Odds ratio will be estimated along with 95% CI. Log-rank tests will be used to compare Kaplan-Meier survival curves associated with patients above and below the median values for the variables of interest. Survival curves are presented with time measured in months. It is important to notice that patient survival will be evaluated every six month through medical record, therefore the Interval-censored survival analysis will be applied which simply extends the approach used for right-censored observations to left- and interval-censored observations (Sun 2006). The probability of a left-censored time is the probability that the true time is less than or equal to the censoring time. And, the probability of an interval-censored observation is the probability that the true time is less than or equal to the upper bound of the interval minus the probability that the true time is less than or equal to the lower bound of the interval. The SAS procedure NPMLE could be used. In addition, we will estimate the optimal cut point of [F] FMISO level using

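### Exploratory OS rests on clinic records alone, with no vital-status check, so some deaths may be missed and survival overstated

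*Combined protocol and SAP*

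**What the plan says.** Section 5.4 states that "we will not be seeing the patients in nuclear medicine after the last imaging is completed". After that, the study relies on "clinical follow-up information from medical records generated at clinic visits and update our data base at 6 month intervals", for two years. Section 7.3 repeats that "patient survival will be evaluated every six month through medical record" and gives the time scale: "Survival is defined from the time of initial PET scan to the last follow up". Because status is updated only every six months, the same section says "the Interval-censored survival analysis will be applied".

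No other source of vital status is named. The only planned telephone call is the 24-hour adverse-event call in Section 5. There is no rule for a patient who stops attending. The Schema adds that "patients will be followed for two years or until disease progression", which leaves open whether a death after progression is sought at all.

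OS is an exploratory endpoint (Section 7.1). It feeds exploratory aim 1.2.a and the Cox, log-rank and ROC analyses in Section 7.3.

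**The concern.** A patient who dies at home, in hospice or at another hospital makes no further clinic visit. Unless someone enters the death in the chart, the analysis sees a patient last known alive at the last contact. Standard survival methods assume that such a patient has the same prognosis as those still under observation. Here the reason for the silence may be the death itself, so the censoring is informative.

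Two things are at stake: the level of the OS curve, and the number of events available to the FMISO-survival models, which is already small. A death not looked for at the time may be hard to recover later.

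**Working it through.** **The plan's own figures.** The documents give no event count, power or hazard ratio for OS. The precision statement in Section 7.2 does reproduce: the Clopper-Pearson interval for 12/20 is 0.3605 to 0.8088, width 0.448. It concerns uptake and has no bearing on OS.

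**Inputs.**
- N = 20 (Section 7.2).
- Two-year enrolment (Section 7.2), with final analysis when accrual is complete (Section 5.4).
- 2-year survival S = 0.63. This is an assumption for this cohort; Section 2.1.b gives 63% as an upper figure for TACE.
- Share of deaths unrecorded, m = 15%, 30% or 50%. This is also an assumption; the documents give no figure.
- Exponential survival, so 24λ = −ln 0.63 = 0.462.

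**Expected deaths.**
- All patients observed for 24 months from the first scan: 20 × (1 − 0.63) = 7.4.
- Analysis at the end of a uniform two-year accrual, so follow-up is spread evenly over 0 to 24 months: 20 × (1 − 0.37/0.462) ≈ 4.0.

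**Deaths lost (m × expected deaths) and apparent 2-year OS.** If missed deaths are censored at about the time of death, the recorded hazard is (1 − m)λ, and apparent OS is 0.63^(1 − m).

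| m | Lost of 7.4 | Lost of 4.0 | Apparent 2-year OS, full follow-up |
|---|---|---|---|
| 15% | 1.1 | 0.6 | 68% |
| 30% | 2.2 | 1.2 | 72% |
| 50% | 3.7 | 2.0 | 79% |

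If those patients were instead carried as alive to 24 months, apparent OS would be 1 − (1 − m) × 0.37, that is 69%, 74% or 82%.

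**Sensitivity to S.** With S = 0.50 or 0.75 and full follow-up, expected deaths are 10 or 5. At m = 25%, recorded deaths are 7.5 or 3.8.

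**Effect on the hazard ratio.** Let m₁ and m₀ be the missed shares in the high- and low-hypoxia groups. The recorded hazard ratio is the true one multiplied by (1 − m₁)/(1 − m₀). If m₁ = m₀ the factor is 1 and there is no bias. If, purely as an illustration, m₁ = 50% and m₀ = 15%, the factor is 0.50/0.85 = 0.59.

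**Effect of lost events on power.** For a median split at 80% power and two-sided 5%, the detectable hazard ratio is exp[(1.96 + 0.84)/√(D/4)], where D is the number of deaths. It is 7.8 at D = 7.4 and 18.4 at D = 3.7.

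**Does interval censoring help?** A death known to lie between updates L and R contributes S(L) − S(R) to the likelihood. A death never recorded contributes only S at the last contact, exactly like a survivor. The method handles an imprecise date; it cannot supply an unknown event.

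**The case against.** The strongest reply is that the text is looser than the concern needs. Section 5.4 says only that patients are not seen in nuclear medicine; routine clinic care goes on. Section 7.3 refers to the medical record generally, and a chart may carry a death notice. Section 7.4 has response categories for early death by cause and for unknown status, so the plan expects deaths to be known. No section says that a patient is censored at the last clinic visit; that is an inference from an undefined rule. This stands as far as it goes: deaths may be missed, not must be. But Section 7.4 classifies response and names no source for deaths, and nothing in the plan requires a death notice to be sought.

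A reader might infer that the FMISO-survival association is itself distorted. The documents do not support that. It requires missed deaths to differ by hypoxia level, and nothing in the plan says whether they would.

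A reader might also take 7.4 deaths as the expected count. That needs 24 months on every patient, whereas Section 5.4 places the final analysis at the end of accrual, where about 4 are expected. Section 2.1.b also reports better survival with TACE plus SBRT than with TACE alone, so the count could be lower still.

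Finally, little depends on OS here. Even with complete ascertainment and full follow-up only a hazard ratio near 7.8 is detectable, and Section 7.3 already calls the analysis exploratory because of the small sample. That is a reason for low severity, not for leaving a known one-directional bias in place.

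**Conclusion.** The concern holds at low severity. The stated source and the open-ended last follow-up allow unrecorded deaths to be censored informatively, and the planned analysis does not correct for it. The direction is known: OS too high, events too few. The size is not known. Under the assumptions above, the loss is between about 0.6 and 3.7 deaths, depending on the missed share and on whether the analysis waits for 24 months of follow-up; apparent 2-year OS with full follow-up is about 68% to 79% against an assumed 63%.

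Without differential missingness, the cost is an inflated Kaplan-Meier level and lost events, not a biased hazard ratio. The primary FMISO-change endpoints and the sample size are unaffected.

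**What to change.** In Sections 5.4 and 7.3, state that:

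- at each six-month update, for any patient without a documented contact in that window, the study team establishes vital status and, where applicable, date of death, by telephone or a public death-record check;
- this continues for the full two years after the last scan, including after progression, and the Schema's follow-up statement is reconciled with it;
- OS is censored at the date the patient was last confirmed alive from any source.

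The cost is at most 20 patients × 4 updates = 80 brief checks by existing staff, and fewer in practice because patients with a documented contact need none. The team should confirm that the consent permits the contact. No extra visit or procedure is needed.

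This does not settle when OS is analysed. Whether the OS analysis waits for two-year follow-up or is run at the end of accrual needs its own statement, because it changes the expected number of deaths from about 4 to about 7.4 under the same assumed survival.

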**Figure 1.**

**Figure 1:** Diagram of patient management and timepoints where the [F] FMISO studies will be done in the course of treatment. FMISO PET #1 will be performed prior to treatment. FMISO PET #2 will be performed 1 month after all TACE procedures (in case multiple TACE procedures are performed) and prior to SBRT, and FMISO PET #3 will be performed 1 month following the end of liver stereotactic radiation therapy. 20 patients will be enrolled in this study.

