### **1.1 Primary Aims:**

- 1.1.a Quantitate HCC tumor hypoxia at baseline using FMISO PET.
- 1.1.b Determine changes in HCC tumor hypoxia and blood flow after TACE, prior to stereotactic radiotherapy.
- 1.1.c Determine changes in treated HCC tumor hypoxia following TACE and radiotherapy.

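### The final analysis is set at the end of accrual, before the last patients can have their third scan and before most or all complete two years of follow-up

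*Combined protocol and SAP*

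**What the plan says.** Section 5.4 plans follow-up from medical records, with staff to "update our data base at 6 month intervals, for two years". The next sentence reads "Final analysis will take place at the completion of patient accrual". Neither protocol nor SAP gives a later data cut-off, a staged analysis or an update after enrolment closes.

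The rest of the plan sets this timetable:

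- **Accrual (7.2):** 20 patients; "We expect to have a full enrollment in 2 years".
- **Scans (Figure 1):** scan 1 is before treatment and scan 2 is one month after the last TACE procedure. For the third, "FMISO PET #3 will be performed 1 month following the end of liver stereotactic radiation therapy".
- **Primary aims (1.1):** aim 1.1.b concerns change after TACE, and aim 1.1.c is to "Determine changes in treated HCC tumor hypoxia following TACE and radiotherapy".
- **Primary analysis (7.3):** changes in HV and T:Bmax "between baseline and 2 follow-up scans will be using paired t-test".
- **Precision (7.2):** the sample size "produces a two-sided 95% confidence interval with a width equal to 0.448 for each FMISO PET scan".
- **Survival (7.1 and 7.3):** overall and disease-free (in 7.3, progression-free) survival are exploratory. Survival is counted from the first scan, and status is checked in the records every six months.

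**The concern.** The trigger sentence conflicts with the plan's own schedule in two ways.

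First, a patient enrolled on the day accrual closes has had at most the baseline scan. Patients enrolled shortly before have at most two scans. The primary change comparisons would lose these pairs for no scientific reason. Baseline aim 1.1.a is not affected.

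Second, accrual and follow-up are both two years long. An analysis at the end of accrual therefore finds almost nobody with the planned follow-up, and the Cox, Kaplan-Meier and interval-censored analyses would use about half of it.

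Some selection is also possible. Scan 2 waits for the last TACE procedure, so among late enrolees those with several procedures are the more likely to lack follow-up scans.

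A lesser wording point belongs with this one. The SCHEMA lets follow-up end at two years or at progression, 5.4 gives two years without mentioning progression, and 7.3 names no stop at progression. The SCHEMA should not be read as ending overall-survival follow-up when disease progresses.

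**Working it through.** **Inputs from the documents.** n = 20 (Figure 1, 7.2); accrual 24 months, expected uptake at least 60%, interval width 0.448, effect size 1.5, alpha 5% (7.2); follow-up 24 months (5.4); two one-month waits before scan 3 (Figure 1).

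**Assumptions.** Entry is even, with patient i entering at month 24(i − 0.5)/20. The lag L from scan 1 to scan 3 is 2 to 6 months. The documents fix only its minimum: 1 + 1 = 2 months, plus the time taken by TACE and SBRT.

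**1. The plan's own figures.** The exact Clopper-Pearson interval for 12/20 is 0.361 to 0.809, width 0.448, so the stated width is reproduced. A two-sided paired t-test with n = 20 and d = 1.5 has power above 0.999, consistent with the stated >80%.

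**2. Patients without follow-up scans at the cut-off.** Time available is 24 minus the entry month. Starting from the last patient this is 0.6, 1.8, 3.0, 4.2, 5.4, 6.6, … months. Count those below L:

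| Lag to scan 3 (months) | 2 | 3 | 4 | 5 | 6 |
|---|---|---|---|---|---|
| Without scan 3, of 20 | 2 | 2 | 3 | 4 | 5 |

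Other even-entry conventions (entry at the start or end of each interval, or first patient on day 0 and last at month 24) give 1 to 5. Accrual over 30 or 36 months gives 1 to 4. With a lag of 1 to 2 months to scan 2, 1 to 2 patients lack scan 2.

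**3. Effect on the primary analyses.** The widths use the Clopper-Pearson beta-quantile formula at exactly 60%, which gives non-integer counts at n = 16 to 18.

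| Patients with scan 3 | 20 | 18 | 17 | 16 | 15 |
|---|---|---|---|---|---|
| Interval width at 60% | 0.448 | 0.471 | 0.484 | 0.499 | 0.514 |
| Effect size for 80% power | 0.66 | 0.70 | 0.72 | 0.75 | 0.78 |

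Power at d = 1.5 is still 0.9997 with 15 pairs.

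**4. Selection, as an illustration only.** Suppose half the patients have a 3-month lag and half a 6-month lag. Then 3/24 = 12.5% and 6/24 = 25% miss scan 3, in expectation 1.25 + 2.5 = 3.75 patients. The longer-lag half makes up 10 × 0.75/(20 − 3.75) = 46% of those scanned, instead of 50%.

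**5. Follow-up for survival.** Counted from enrolment and capped at 24 months, with midpoint entry for the mean and all four entry conventions for the count:

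| Accrual (months) | 24 | 30 | 36 |
|---|---|---|---|
| Patients reaching 24 months, of 20 | 0–1 | 4–5 | 6–7 |
| Mean follow-up (months) | 12.0 | 14.4 | 16.0 |

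At 24-month accrual this is 20 × 12 = 240 of 480 planned person-months.

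**6. Deaths observed, as an illustration only.** Take a constant hazard h = −ln(S)/24, where S is two-year survival, and expected deaths Σ[1 − exp(−h × min(follow-up, 24))]. For 24-month accrual:

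- S = 0.80: 2.07 against 4.0 with full follow-up, a loss of 48%.
- S = 0.63 (the upper figure for TACE in 2.1.b): 3.98 against 7.4, a loss of 46%.
- S = 0.50: 5.57 against 10.0, a loss of 44%.

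At 36-month accrual the loss is still 1 − 2.72/4.0 = 32% for S = 0.80 and 1 − 7.05/10.0 = 29.5% for S = 0.50.

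**The case against.** **Loose wording.** The trigger follows directly on a two-year plan of record updates, and 7.3 needs all three scans, so the authors may have meant one analysis once the data are complete. That is possible, but 7.2 uses accrual for enrolment, and a team following 5.4 literally would analyse too early. What stands is that the loss occurs only if the sentence is followed as written.

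**Small effect on the primary test.** This stands. Power at the planned effect size is untouched, and the cost is precision.

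**The interval width depends on the proportion.** With uptake above 60%, the width can stay below 0.448 despite missing scans; 12/15 gives 0.438. That is correct, but 0.448 is itself the width at 60%. At 80% the full sample would give 0.379 (16/20), so the loss relative to 20 patients remains.

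**Selection and deaths lost rest on invented inputs.** No passage gives a distribution of lags or the survival expected in this population. The selection illustration moves the mix by less than one patient and does not support a claim of material bias. The deaths figures largely restate that follow-up is halved. Both are illustrations, and the conclusion does not depend on them.

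**Slower accrual helps.** It does: with 48-month accrual about 10 of 20 would reach two years. The last enrolee still lacks scan 3 under any accrual pattern.

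**Conclusion.** The concern holds and should be fixed. That the last enrolees lack scan 3 follows from Figure 1 and 5.4 alone. The count, 2 to 5 of 20 with midpoint entry (1 to 5 across entry conventions), assumes even accrual over 24 months and a lag of 2 to 6 months. Precision at scan 3 then falls short of the 0.448 stated in 7.2 at 60% uptake, reaching 0.514 in the worst case, while the stated power is kept.

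At the stated accrual period at most 1 of 20 patients completes two years counted from enrolment, and none does if the two years run from the last scan. The exploratory survival analyses are weakened, not invalidated. Response is not tied to the two-year follow-up, and baseline aim 1.1.a is unaffected.

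**What to change.** Replace the trigger sentence in 5.4 with two:

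- The primary imaging analysis takes place once the last enrolled patient has had FMISO scan 3 or has left the study.
- The exploratory survival analysis takes place once the last patient has completed the planned two years of record follow-up.

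The response analysis need not wait for the two years. Separately, reconcile the SCHEMA with 5.4 and 7.3 by stating that vital status is collected from records for two years whether or not disease has progressed. Say also whether the two years run from the first scan or from the end of imaging.

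The cost is wording and waiting. With 24-month accrual, the imaging analysis moves to about month 24 + L, that is months 26 to 30 for the assumed lags. The survival analysis moves to about month 24 + 24 = 48, or months 50 to 54 if the two years run from the last scan. No patient, scan or visit is added, because the record review is already planned.
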